Prevalence and characteristics of somatic symptom disorder in the elderly in a community-based population: a large-scale cross-sectional study in China

Assessment of Somatic Symptom in Chinese Community-Dwelling People

Protocol Number	SSSCN202011
NCT No.	NCT04815863
Date	Sep 20, 2018

STUDY PROTOCOL SYNOPSIS

Title	Prevalence and characteristics of somatic symptom disorder in the elderly in a community-based population: a large-scale cross-sectional study in China
Sponsor	Investigator-Initiated Trial (IIT)
Primary Objectives	
 1. to clarify the prevalence of somatic symptom disorder (SSD), depressive disorders, and anxiety disorders in the elderly in China; 2. to identify physical and psychological differences between the elderly and non-elderly; 3. to explore risk factors for SSD in the elderly.
Study Design	
This prospective cross-sectional study (Assessment of Somatic Symptom in Chinese Community-Dwelling People, ClinicalTrials.gov identifier NCT04815863, registered on 06/12/2020) is a multicenter registry conducted in Shanghai, China, under the supervision of the Shanghai Association of Chinese Integrative Medicine.
 
A multistage and stratified systematic sampling technique will be used to choose representative districts from sixteen districts in Shanghai, which are then divided into low, medium, and high economic levels according to the per capita gross domestic product of each district in 2018. Eleven districts will be selected proportionally and randomly and represented by 105 community health service institutions. The study was approved by institutional review committees at each center. The study is compliant with the 1975 Declaration of Helsinki guidelines.
 
(1) assessment of somatic symptom disorder (SSD)
 
The Somatic Symptom questionnaire is self-administered with an abbreviated 20-item measure. Briefly, it is composed of four dimensions: physical disorders, depressive disorders, anxiety disorders and depressive and anxiety disorders. Half of the items ask about physical complaints (one item per body system). SSS-CN scores ranging from 20 to 29, 30–39, 40–59 and ≥ 60 correspond to normal, mild, moderate and severe SSD, respectively.
 
(2) assessment of depressive and anxiety disorders
 
All participants will be assessed for depressive and anxiety disorders according to the PHQ-9 and GAD-7, which evaluate the frequencies at which certain symptoms had been experienced over the last two weeks, ranging from 0 ('not at all') to 3 ('nearly every day'). The cutoff values are listed below. For PHQ-9, scores of 5–9 indicate mild depressive disorder, 10–14 indicate moderate depressive disorder, 15–19 indicate moderately severe depressive disorder and ≥ 20 indicate severe depressive disorder. For GAD-7, scores range from 0 to 21, with scores of 5–9, 10–14, and ≥ 15

	
representing mild, moderate, and severe anxiety symptom levels, respectively.
 
(3) sociodemographic and clinical characteristics
 
Sociodemographic data, including age, gender, level of education and marital status, will also be collected. A semi-structured questionnaire concerning clinical characteristics will be administered to survey participants' medical and medication histories.

Number of Subjects	
Enrollment: 9110 [anticipate]
 
Elderly group: 6874 [anticipate]
 
Non-elderly group: 2236 [anticipate]

Enrollment Criteria	
Inclusion criteria were:
 
(1) voluntary participation and provision of written consent to participate in the study's evaluation and assessment;
 
(2) completion of the SSS-CN questionnaire, Patient Health Questionnaire-9 (PHQ-9) and Generalized Anxiety Disorder-7 (GAD- 7) questionnaires.
 
Exclusion criteria were :
 
(1) patients lacking self-assessed abilities or who refused to participate;
 
(2) patients who have been previously confirmed to have serious mental disorders, mental retardation, or dementia;
 
(3) patients with cancer or central nervous system diseases;
 
(4) patients with any missing data within questionnaire items or with more than one item missing from sociodemographic information;
 
(5) patients with any medical conditions that in the opinion of the investigators will not be appropriate to participate in the study.

Safety Assessment	Adverse events were not required in this study protocol.
Endpoints	
1. Number of Participants With Somatic Symptoms Disorder
 
2. Number of Participants With Somatic Symptoms Disorder Accompanied With Anxiety
 
3. Number of Participants With Somatic Symptoms Disorder Accompanied With Depression

Statistical Analysis	
Descriptive statistics for each group, such as counts and percentages (%) for non-continuous variables, will be reported for all sociodemographic and clinical characteristics. The prevalences of SSD of various severities for different genders and for participants diagnosed with depressive and anxiety disorders will be calculated. In order to assess whether SSD, depressive and anxiety disorders are associated with aged groups and whether depressive and anxiety disorders are associated with the severity of SSD, binary logistic regressions will be performed, adjusting for gender, educational level (middle school and below, high school, college, master and above), marital status (never married, married, divorced, widowed), hypertension (yes/no), diabetes mellitus (yes/ no), CV disease

	
(yes/no), endocrine and metabolic disease except DM (yes/no), other diseases (yes/no), surgery (yes/no) and antipsychotic intake (yes/no) in all models.
 
Univariate analyses and binary logistic regression models will be used to assess the effects of sociodemographic factors and clinical characteristics on SSD in the non- elderly and elderly. Categorical sociodemographic and clinical variables will be analyzed by chi-square test. Binary logistic regressions will be performed using SSD (yes/no) as the dependent variable, adjusting for gender, educational level, marital status, and antipsychotic intake.
 
Fisher's exact test was used instead of the chi-square test only when one or more expectations for each cell of the 2-by-2 tables was below 5. A significance level was set at a p-value < 0.05 (two-tailed). Missing data were imputed with a multiple imputation approach. All statistical analyses were performed with SPSS 22 (IBM SPSS Statistics for Windows, Version 22.0. Armonk, NY: IBM Corp).

--	---

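### Objective 1 promises a national prevalence of disorders in the elderly, but the design supports only screen-positive proportions among eligible elderly people reached through the sampled Shanghai institutions, and two of its three prevalences have no endpoint or planned estimate

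*Combined protocol and SAP*

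**What the plan says.** Under Primary Objectives in the Synopsis, the first aim is "to clarify the prevalence of somatic symptom disorder (SSD), depressive disorders, and anxiety disorders in the elderly in China".

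Under Study Design, the study "is a multicenter registry conducted in Shanghai, China". On sampling, "A multistage and stratified systematic sampling technique will be used to choose representative districts from sixteen districts in Shanghai", and then "Eleven districts will be selected proportionally and randomly and represented by 105 community health service institutions". The text does not say how institutions are chosen within districts, or people within institutions.

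The same section defines cases by score. SSS-CN bands starting at 20, 30, 40 and 60 "correspond to normal, mild, moderate and severe SSD, respectively". For PHQ-9, "scores of 5–9 indicate mild depressive disorder", with higher bands for more severe disorder. The GAD-7 bands are described differently, as "representing mild, moderate, and severe anxiety symptom levels, respectively". Statistical Analysis later refers to participants as diagnosed with these conditions.

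Enrollment Criteria limits participants to consenting people who complete all three questionnaires. It excludes those unable to self-assess, those with known serious mental disorder, intellectual disability or dementia, those with cancer or central nervous system disease, and anyone the investigators judge unsuitable.

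Endpoints lists three counts: SSD, SSD with anxiety, and SSD with depression. The sentence in Statistical Analysis that plans prevalences covers SSD only, by severity, by gender and among participants with depression or anxiety.

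**The concern.** A prevalence claim has to fit three things: the population sampled, the way a case is identified, and the estimates that the analysis will produce. Objective 1 goes beyond the plan on all three. It names China where the frame is one city. It names disorders where the measurement is a questionnaire band. It names three prevalences where the endpoints and the prevalence sentence deliver one.

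If the plan is followed as written, the report would answer its first primary objective with a statement about disorders in the elderly population of China that the data cannot support. A reader could take a PHQ-9 score of 5 for a diagnosed depressive disorder, because the labels change between sections. Depression and anxiety overall in the elderly might not be reported at all. The prevalences that are reported would carry no planned measure of precision, although participants are recruited in clusters.

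**Working it through.** **Population.** Objective 1 names the elderly in China. The first-stage frame in Study Design is Shanghai's sixteen districts, and nothing outside Shanghai is sampled. Statistical Analysis contains no weights and no standardisation to a national population. The location wording in the title could be read as only saying where the work is done. Objective 1 cannot, because it names the population whose prevalence is to be established. Within Shanghai, the eligibility rules narrow the group further, and no age limit for elderly is given.

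**Case status.** The bands are stated openly, and the lowest positive scores follow from them: SSS-CN ≥30 (because 20–29 is normal), PHQ-9 ≥5 and GAD-7 ≥5. No diagnostic interview, criteria, validation subsample or correction for misclassification is described. The result is the proportion at or above a score, under three different labels: disorder for SSS-CN and PHQ-9, symptom level for GAD-7, and diagnosed in the analysis text.

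**Coverage of objective 1.**
- SSD: endpoint 1 and the prevalence sentence.
- Anxiety overall: none. Endpoint 2 counts it only jointly with SSD.
- Depression overall: none. Endpoint 3 counts it only jointly with SSD.

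**Sample size.** The stated total reproduces: 6874 + 2236 = 9110. No expected prevalence, precision target or design effect is given, so no derivation can be checked.

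**Precision (illustration only).** Inputs from the documents are 6874 elderly people and 105 institutions. Assumed inputs are equal cluster sizes, an intra-institution correlation (ICC) of 0.01, 0.02 or 0.05, and a prevalence of 20%.
- Mean cluster size m = 6874/105 = 65.47.
- Design effect = 1 + (m − 1) × ICC = 1.64, 2.29, 4.22.
- Width multiplier = square root of the design effect = 1.28, 1.51, 2.06.
- Simple half-width = 1.96 × √(0.20 × 0.80/6874) = 0.95 percentage points.
- Half-width allowing for clustering by institution = 1.21, 1.43, 1.94 points.

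District-level correlation and the small number of districts would widen this further. Stratification and the 11-of-16 sampling fraction would narrow it. None of these is included.

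**Misclassification (illustration only).** The screen-positive proportion is Se × p + (1 − Sp) × (1 − p). With sensitivity and specificity each assumed to be 0.80 or 0.90, a true 10% gives 17% (0.8 × 0.1 + 0.1 × 0.9) to 27% (0.9 × 0.1 + 0.2 × 0.9). These accuracies are not in the documents. The example shows only that a sample of 6874 does not limit this kind of error.

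**The case against.** The strongest reply is that the plan is more open, and closer to adequate, than the objective's wording suggests. The score bands are set out in full, so diagnosed can be read as meeting a band. Districts are selected at random with regard to economic level. The regressions in Statistical Analysis relate SSD, depression and anxiety to age group, which requires case status for each condition in each group.

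Much of this stands. Depression and anxiety are measured and analysed, so a reader who infers that they are missing outcomes goes too far: what is missing is a planned prevalence estimate. The operational definition is disclosed, so the fault is the label and the claim, and nothing is concealed. The reply does not rescue the national claim, because random selection of Shanghai districts supports inference to Shanghai at most. Nor does disclosing a cutoff turn a screening score into a disorder prevalence.

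Two stronger readings are tempting. A reader might infer that the 2236 non-elderly participants would distort the elderly prevalence through a pooled figure. The endpoints do not state an age restriction, but no section plans to report a pooled figure as the elderly result, and Statistical Analysis examines SSD in the elderly and the non-elderly. A reader might also count the five unselected districts as an error. Leaving some units out is ordinary sampling; the step that lacks support is from Shanghai to China.

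**Conclusion.** The point holds as a mismatch between objective 1 and what the design and analysis can deliver. The Shanghai frame, the absence of a diagnostic step, and the lack of an endpoint or planned estimate for two of the three prevalences can all be read directly from the Synopsis and need no assumption. So can the absence of any confidence interval for a prevalence and of any mention of clustering.

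The gap between the Shanghai screen-positive proportion and the national disorder prevalence cannot be quantified from the documents. A reader might infer that the study will overstate national prevalence. The documents do not support that: they give no questionnaire accuracy and no comparison of Shanghai with the rest of China, and the effect of the exclusions is unknown.

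The widening of about 1.3 to 2.1 times rests entirely on the assumed ICC of 0.01 to 0.05 and equal cluster sizes. It shows why the interval method should be specified and is not a forecast. The data remain usable. The objective, endpoints and interval method should be corrected before results are reported.

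**What to change.** 1. Restate objective 1 as three separate proportions: SSS-CN ≥30, PHQ-9 ≥5 and GAD-7 ≥5, each among eligible community-dwelling elderly people reached through the sampled Shanghai institutions. State the age limit, confine conclusions to that population, and add Shanghai to the title.
2. Use screening-positive wording throughout. This includes the reference to diagnosed participants in Statistical Analysis, the yes/no SSD outcome in the regression models, and objective 3.
3. Add PHQ-9 positivity and GAD-7 positivity in the elderly as endpoints, and report endpoints 1 to 3 by age group.
4. Give each prevalence a 95% confidence interval that accounts for clustering by institution and district. Where selection probabilities are known, use the corresponding weights. Otherwise state that the sample is assumed to be self-weighting. In that case, also state that the interval does not cover selection bias.

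Rows for moderate-or-worse bands are optional; the plan already reports SSD by severity.

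The cost is rewording, a few table rows, and a survey-type interval that needs institution and district identifiers plus either selection probabilities or the stated assumption. No new participants or instruments are required. The downside is a narrower headline claim and wider intervals. Relabelling does not remove misclassification or selection bias; it keeps the conclusion within what was measured.

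### Participants are sampled through 11 districts and 105 institutions, but the tests and regressions treat them as independent and no confidence interval is planned for the primary prevalences

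*Combined protocol and SAP*

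**What the plan says.** The first primary objective is "to clarify the prevalence of somatic symptom disorder (SSD), depressive disorders, and anxiety disorders in the elderly in China". Under Study Design, the sampling is described thus: "A multistage and stratified systematic sampling technique will be used to choose representative districts from sixteen districts in Shanghai". It continues: "Eleven districts will be selected proportionally and randomly and represented by 105 community health service institutions". People therefore enter the study through institutions nested in districts.

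The listed endpoints are counts, the first being "Number of Participants With Somatic Symptoms Disorder". The Statistical Analysis section has one sentence on prevalence: "The prevalences of SSD of various severities for different genders and for participants diagnosed with depressive and anxiety disorders will be calculated". It attaches no interval or standard error.

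The comparisons are ordinary ones. Adjusted binary logistic regressions are planned "In order to assess whether SSD, depressive and anxiety disorders are associated with aged groups", with gender, education, marital status, six medical-history items and antipsychotic intake as covariates. For risk factors, "Categorical sociodemographic and clinical variables will be analyzed by chi-square test", followed by a logistic regression with a shorter covariate list. Significance is two-sided at 0.05. The document mentions no institution, district or economic-level term, random effect, generalised estimating equation (GEE), robust variance or design effect.

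**The concern.** People who use the same institution tend to resemble one another in income, morbidity and local practice. The design itself groups districts by economic level, which suggests that areas are expected to differ. Where outcomes correlate within institutions, 6874 elderly participants carry less information than 6874 independent people, and formulas that assume independence overstate precision.

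Two things are at stake. The main one is the first objective: a prevalence with no stated precision is hard to use, and the interval that an analyst would add by default would be too narrow. The second is the p-values. They would be too small for any factor whose mix also differs between institutions, most clearly in the univariate chi-square tests.

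**Working it through.** **Inputs from the synopsis.** 9110 participants = 6874 elderly + 2236 non-elderly (the sum checks); 105 institutions; 11 of 16 districts. No prevalence, precision target, power or ICC is given, so the sample size itself cannot be reproduced.

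**Assumed inputs.** ICC 0.01, 0.02 and 0.05; SSD prevalence 20%; equal institution sizes unless stated.

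**1. Elderly prevalence.** The mean cluster size is m = 6874/105 = 65.47. The design effect is DEFF = 1 + (m − 1) × ICC. An ordinary 95% interval then covers 1 − 2Φ(−1.96/√DEFF). The ordinary half-width is 1.96 × √(0.2 × 0.8/6874) = 0.95 points; the correct one is √DEFF times that. With unequal sizes (coefficient of variation 0.5), DEFF = 1 + (1.25m − 1) × ICC.

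| ICC | DEFF | Coverage of ordinary interval | Correct half-width (points) | DEFF, unequal sizes |
|---|---|---|---|---|
| 0.01 | 1 + 64.47 × 0.01 = 1.64 | 87% | 1.21 | 1.81 |
| 0.02 | 1 + 64.47 × 0.02 = 2.29 | 80% | 1.43 | 2.62 |
| 0.05 | 1 + 64.47 × 0.05 = 4.22 | 66% | 1.94 | 5.04 |

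A simulation at an assumed prevalence of 30% gave coverage of about 88%, 80% and 66%.

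**2. Planned chi-square tests within the elderly.** For a binary factor whose own within-institution correlation is ρx, DEFF = 1 + (m − 1) × ICC × ρx, and the true type I error at nominal 5% is 2Φ(−1.96/√DEFF). Example: ICC 0.02 and ρx 0.30 give 1 + 64.47 × 0.02 × 0.30 = 1.387, then 1.96/√1.387 = 1.664 and 9.6%.

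| ρx | ICC 0.01 | ICC 0.02 | ICC 0.05 |
|---|---|---|---|
| 0 | 5.0% | 5.0% | 5.0% |
| 0.10 | 5.7% | 6.5% | 8.8% |
| 0.30 | 7.3% | 9.6% | 16.2% |

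Simulation (4,000 runs) gave 5.0/5.3/5.2%, 6.2/7.0/8.9% and 6.6/9.4/17.0% for the three rows.

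**3. Planned adjusted comparison of elderly and non-elderly.** The model has 1 (age group) + 1 (gender) + 3 (education) + 3 (marital status) + 7 (clinical yes/no items) = 15 slopes. It was simulated with 9110 people, 105 near-equal institutions, no age effect, assumed covariate frequencies and effects, and 4,000 replicates per scenario (Monte Carlo standard error 0.3 to 0.6 points). Type I error at ICC 0.01/0.02/0.05, where ρx is the within-institution correlation of age group:

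| Between-institution variation explained by the covariates | ρx 0.10 | ρx 0.30 |
|---|---|---|
| None | 6.3/5.9/8.4% | 7.2/9.3/16.3% |
| Half, in both SSD and age mix | 5.8/5.1/6.4% | 5.2/6.3/8.5% |

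Institution-clustered standard errors gave 4.4% to 6.0%, with no district correlation in that simulation. It was not replicated independently, and the small dips as ICC rises are within simulation error.

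**4. The district level.** Let ρd be the correlation between elderly people in different institutions of one district. It adds (105/11 − 1) × m × ρd to DEFF. At ICC 0.02, ρd = 0.001 adds 0.56 (total 2.85) and ρd = 0.005 adds 2.80 (total 5.09). An institution-clustered interval reflects only 2.29, so it covers 2Φ(1.96 × √(2.29/2.85)) − 1 = 92%, or 81% with 5.09. A simulation with 20,000 replicates and no finite-population correction, at ρd 0/0.001/0.005, gave:

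- ordinary interval: 80.3/75.7/61.6%;
- institution-clustered: 95.1/92.3/81.2%;
- district-clustered, t on 10 degrees of freedom: 94.9/95.1/94.9%, half-width 1.58/1.77/2.36 points (institution-clustered half-width at ρd 0: 1.44).

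If the target is only Shanghai's 16 districts, 11/16 of the district component (624.9 × ρd = 0.625 or 3.125) drops out. DEFF becomes 2.42 or 2.94, and institution-clustered coverage rises to 94.3% or 91.6%.

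**The case against.** The coverage figures describe an interval that the plan does not contain. Strictly, the text shows only that precision goes unreported, and in a synopsis silence is weaker evidence than a wrong method. Every ICC and correlation here is assumed. At the middle ICC the half-width grows from 0.95 to 1.43 points, and no threshold or precision target in the plan would be overturned. The adjusted age-group test is barely affected at modest correlations, and the risk-factor objective is exploratory.

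Much of this stands as a limit on size. The harm is conditional, and the larger type I errors need a factor correlation of 0.30, mostly with ICC 0.05. An unadjusted age-group comparison would look worse, but the plan does not make one, so it is left out here. It also stands that the target population matters. For Shanghai's 16 districts alone, institution clustering comes close to nominal coverage, while an uncorrected district-clustered interval is too wide (about 96% to 98.5% coverage at ρd 0.001 to 0.005). A clustered interval does not replace weighting where selection probabilities differ; that is a separate question.

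The objection does not remove the defect. This is the only analysis plan in the documents, and it is specific enough to list covariate categories and a rule for Fisher's test. The tests it names do assume independence. An unknown ICC favours a clustered variance, which estimates the dependence from the data and costs little if there is none. A large sample gives no protection, because at a fixed ICC the design effect grows with institution size.

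**Conclusion.** The concern holds and should be fixed. The sample is clustered, the planned tests and regressions ignore this, and the prevalences have no planned interval. The main consequence is for the first objective. Under the assumed ICC range of 0.01 to 0.05, an ordinary 95% interval would really cover 87% down to 66%, and the correct half-width is about 1.3 to 2.1 times the ordinary one (√1.64 to √4.22). Inflation in the chi-square tests runs from slight (about 6%) to substantial (about 16%), depending on how unevenly the factor is spread. The adjusted age-group test stays at 5.1% to 6.3% at ICC 0.01 to 0.02 and correlation 0.10.

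These sizes depend on the assumed ICC, prevalence, factor correlations and near-equal institution sizes; unequal sizes make matters worse. The direction depends only on a positive within-institution correlation and, for the tests, on a factor whose mix differs between institutions. Nothing here implies that the point estimates are wrong.

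**What to change.** 1. Record and keep the institution and district of each participant.
2. State whether the target is Shanghai's 16 districts, where a finite-population correction is possible, or a wider population. State also whether the economic levels were formed before the districts were selected.
3. Report each prevalence with a 95% interval that allows for clustering by institution.
4. Replace the ordinary tests with Rao-Scott chi-square tests, and the ordinary regressions with cluster-robust or GEE logistic regression, clustered by institution. Where imputation is used, fit within each imputed dataset and pool. For an imputed factor, use a one-factor cluster-robust logistic regression in place of Rao-Scott, so that estimates and variances can be pooled. Institution is the main level because 11 districts cannot support a joint test of 15 slopes.
5. That reason does not apply to a single prevalence, and institution clustering misses any further district correlation. So add a district-clustered sensitivity analysis for the prevalences and the elderly versus non-elderly coefficient, with a small-sample correction. Use about 8 degrees of freedom (11 districts − 3 levels; critical t 2.31) if the levels preceded selection, or about 10 (11 − 1; 2.23) if not. Show both prevalence intervals side by side.

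The cost is low if the identifiers exist. This needs confirming: the data list under Study Design names neither, though it need not be complete. Prevalence intervals need no imputation, because the exclusion criteria remove "patients with any missing data within questionnaire items or with more than one item missing from sociodemographic information", so SSD, PHQ-9 and GAD-7 status are complete. The price is wider intervals, some loss of nominal significance, and little power in the district analysis.

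### The elderly prevalence has no weighting or standardisation, and the multistage selection is not shown to be self-weighting

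*Combined protocol and SAP*

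**What the plan says.** The first primary objective (Synopsis, Primary Objectives) is "to clarify the prevalence of somatic symptom disorder (SSD), depressive disorders, and anxiety disorders in the elderly in China".

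On selection, Synopsis, Study Design says: "A multistage and stratified systematic sampling technique will be used to choose representative districts from sixteen districts in Shanghai". The districts are "divided into low, medium, and high economic levels according to the per capita gross domestic product of each district in 2018". It continues: "Eleven districts will be selected proportionally and randomly and represented by 105 community health service institutions". It does not explain what the proportionality refers to, how many districts fall in each economic level, or how the 105 institutions are picked.

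On people, Enrollment Criteria asks for "voluntary participation and provision of written consent to participate in the study's evaluation and assessment" and completed questionnaires. No list of residents, sampling interval, quota or number per site is given. Number of Subjects anticipates 6874 elderly and 2236 non-elderly, 9110 in all.

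On analysis, the Endpoints are numbers of participants with each condition. Statistical Analysis promises "counts and percentages (%) for non-continuous variables" for the sociodemographic and clinical characteristics, and says of prevalences only that they are to be calculated. No selection weight, post-stratification, standardisation or survey procedure is named. The logistic regressions adjust for covariates, but district economic level is not among them, and they are not set up to produce a population prevalence.

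**The concern.** A plain sample percentage estimates a population prevalence without bias in general only if every elderly resident covered by the design has the same overall chance of being in the sample. That chance is the product of the probabilities at the district, institution and person stages. If it differs between people, groups recruited more heavily than their population share pull the estimate towards their own prevalence.

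The plan stratifies by district economic level, so it treats that level as relevant to representativeness. The analysis then makes no use of it. Nothing requires a site's recruitment to follow the size of the elderly population it serves.

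At stake is the point estimate for the first objective, not the width of its confidence interval. A larger sample would not reduce this error.

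**Working it through.** **1. The plan's own figures.** 6874 + 2236 = 9110, so the enrolment figures agree. The documents give no assumed prevalence, target precision, selection probability or weight, so there is no planned estimate to reproduce. On average, 6874 / 105 = 65.5 elderly per institution and 6874 / 11 = 624.9 per district. These are averages; no take per site is fixed.

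**2. Is the district stage self-weighting?** It depends on how the procedure is read.

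- *Whole districts drawn with equal probability within three separate strata.* Equal fractions need 11 × N_h / 16 to be a whole number in each stratum of N_h districts. Since 11 and 16 share no factor, N_h would have to be a multiple of 16, which is impossible with three non-empty strata. Over the 21 possible splits of 16, the best allocation leaves a highest-to-lowest fraction ratio between 1.05 (strata 3/3/10) and 1.67 (1/5/10). Strata of 5/5/6 with 4/3/4 drawn give fractions 0.80/0.60/0.67, a ratio of 0.80 / 0.60 = 1.33.
- *One systematic pass over a list ordered by economic level, interval 16/11.* Every district has probability 11/16 = 0.6875.

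The text is compatible with both readings.

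**3. The later stages.** Even with equal district probabilities, equal overall probability must also hold for institutions and people. The documents give no probability for either stage, so self-weighting is not shown.

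**4. What an unweighted percentage estimates.** With population shares P_h, sample shares s_h and prevalences p_h:

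- raw = Σ s_h p_h
- population value = Σ P_h p_h
- bias = Σ (s_h − P_h) p_h

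The bias is zero if the p_h are all equal or if s_h = P_h.

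**5. Illustration.** All shares and prevalences here are assumed; none is in the documents. P = 30/40/30%, s = 45/35/20%.

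| Prevalence by level | Raw | Population | Error |
|---|---|---|---|
| 20/28/36% | 0.45×20 + 0.35×28 + 0.20×36 = 26.0% | 0.30×20 + 0.40×28 + 0.30×36 = 28.0% | −2.0 points |
| 36/28/20% | 0.45×36 + 0.35×28 + 0.20×20 = 30.0% | 28.0% | +2.0 points |
| 22/26/30% | 0.45×22 + 0.35×26 + 0.20×30 = 25.0% | 0.30×22 + 0.40×26 + 0.30×30 = 26.0% | −1.0 point |

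Simple standard error at 28% with n = 6874: √(0.28 × 0.72 / 6874) = 0.0054, or 0.54 points.

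**6. How much of this could come from the district fractions alone?** The sample-to-population ratios assumed in step 5 are 45/30 = 1.50, 35/40 = 0.875 and 20/30 = 0.667, a spread of 1.50 / 0.667 = 2.25. That is wider than anything in step 2. Take instead strata of 5/5/6 with 4/3/4 drawn, and assume equal district populations and equal takes. The differences s_h − P_h are 4/11 − 5/16 = 0.051, 3/11 − 5/16 = −0.040 and 4/11 − 6/16 = −0.011. With prevalences 20/28/36% the bias is 8 points times the difference between the outer two values. Its absolute size runs from 8 × (0.0398 − 0.0114) = 0.23 to 8 × (0.0511 + 0.0398) = 0.73 points, depending on which stratum is under-drawn. With 22/26/30% it is half that, 0.11 to 0.36 points.

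**7. Price of weighting in the step 5 example.** Kish factor = Σ P_h² / s_h = 0.09/0.45 + 0.16/0.35 + 0.09/0.20 = 0.200 + 0.457 + 0.450 = 1.107. The standard error rises from 0.54 to 0.54 × √1.107 = 0.57 points.

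**The case against.** A reader might infer from the draw of 11 from 16 that the design cannot be self-weighting. The documents do not support that. The divisibility argument covers the district stage only, and only under separate equal-probability draws within strata. The synopsis describes the technique as systematic and the selection as proportional. A single systematic pass gives every district 11/16, and size-proportional selection or compensating fractions at later stages could equalise the overall probabilities. This part of the objection stands: the supportable statement is that self-weighting is not shown.

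A reader might also take the 2-point error as a consequence of the district fractions. It is not. It comes from the assumed unequal recruitment; the 5/5/6 split alone gives well under a point.

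The plan does not say outright that prevalences will be raw percentages. The sentence on counts and percentages concerns sociodemographic and clinical characteristics. The inference rests on endpoints defined as numbers of participants and on the absence of any weight. It is reasonable, but it is an inference.

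Finally, full inverse-probability weights may be impossible. Participation is voluntary and no person-level frame is given, so dividing the number sampled by the catchment would treat volunteers as a random sample. That limits the remedy but does not remove the concern, because post-stratification remains available.

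**Conclusion.** The concern holds in this form: objective 1 is a population quantity, the plan names no weighting or standardisation, and nothing shows that the selection is self-weighting through all three stages. Following the plan as written gives a percentage in which districts and institutions count by recruitment volume.

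Whether that figure is biased depends on whether prevalence varies with recruitment share relative to population share. The documents give no prevalence by district, institution or age, so the size is unknown and could be zero. The errors of 1.0 and 2.0 points, about two to four simple standard errors, rest entirely on the assumed shares and prevalences. They show only that an ordinary recruitment imbalance could outweigh the sampling error at this sample size.

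This is a cheap improvement to the primary estimate, not evidence that the estimate is wrong.

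**What to change.** 1. In Study Design, state the number of districts per economic level, what the proportional selection refers to, how institutions are chosen, how people are approached within them, and whether the take per site is fixed or proportional to catchment.
2. In Statistical Analysis, define the objective 1 estimate as the prevalence post-stratified to the Shanghai resident elderly by age band, gender and district economic level. Report the raw percentage beside it. Age and gender are already collected, and economic level follows from the district.
3. Add design weights for the district and institution stages where the selection probabilities are known. Use person-level inverse-probability weights only if a person-level frame exists. If it does not, say that participants are volunteers and that post-stratification corrects only for the variables used.
4. If the investigators hold that the design is self-weighting, give the probability at each stage so that this can be checked.

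Cost: population counts for the post-stratification cells from an external source, one weighting step, and some loss of precision (Kish factor about 1.11 in the assumed example). The synopsis does not give the age that defines the elderly group; it must be fixed before the cells can be drawn up. No extra participants are needed.
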